Diarrhea Adult and Pediatric ≥ 1 Year  Pediatric < 1 Year	Transient or intermittent episodes of unformed stools OR Increase of ≤ 3 stools over baseline/24 hr  Liquid stools (more unformed than usual) but usual number of stools	Persistent episodes of unformed to watery stools OR Increase of 4–6 stools over baseline per 24 hrs.  Liquid stools with increased number of stools OR Mild dehydration	Bloody diarrhea OR Increase of ≥ 7 stools per 24-hour period OR IV fluid replacement indicated  Liquid stools with moderate dehydration	Life-threatening consequences (e.g., hypotensive shock)  Liquid stools resulting in severe dehydration with aggressive rehydration indicated OR Hypotensive shock
Dysphagia-Odynophagia	Symptomatic but able to eat usual diet	Symptoms causing altered dietary intake without medical intervention indicated	Symptoms causing severely altered dietary intake with medical intervention indicated	Life-threatening reduction in oral intake

GASTROINTESTINAL				
	Grade 1	Grade 2	Grade 3	Grade 4
Mucositis/Stomatitis (clinical exam) See also Proctitis, Dysphagia-Odynophagia	Erythema of the mucosa	Patchy pseudomembranes or ulcerations	Confluent pseudomembranes or ulcerations OR Mucosal bleeding with minor trauma	Tissue necrosis OR Diffuse spontaneous mucosal bleeding OR Life-threatening consequences (e.g., aspiration, choking)
Nausea	Transient (< 24 hours) or intermittent nausea with no or minimal interference with oral intake	Persistent nausea resulting in decreased oral intake for 24-48 hours	Persistent nausea resulting in minimal oral intake for > 48 hours OR Aggressive rehydration indicated (eg, IV fluids)	Life-threatening consequences (e.g., hypotensive shock)
Pancreatitis	NA	Symptomatic AND Hospitalization not indicated (other than ER visit)	Symptomatic AND Hospitalization indicated (other than ER visit)	Life-threatening consequences (e.g., sepsis, circulatory failure, hemorrhage)
Proctitis (functional-symptomatic) Also see Mucositis/Stomatitis for Clinical Exam	Rectal discomfort AND No intervention indicated	Symptoms causing greater than minimal interference with usual social & functional activities OR Medical intervention indicated	Symptoms causing inability to perform usual social/functional activities OR Operative intervention indicated	Life-threatening consequences (e.g., perforation)
Vomiting	Transient or intermittent vomiting with no or minimal interference with oral intake	Frequent episodes of vomiting with no or mild dehydration	Persistent vomiting resulting in orthostatic hypotension OR Aggressive rehydration indicated	Life-threatening consequences (e.g., hypotensive shock)

NEUROLOGICAL				
	Grade 1	Grade 2	Grade 3	Grade 4
Alteration in Personality-Behavior or in Mood (eg, agitation, anxiety, depression, mania, psychosis)	Alteration causing no or minimal interference with usual social & functional activities	Alteration causing greater than minimal interference with usual social & functional activities	Alteration causing inability to perform usual social & functional activities	Behavior potentially harmful to self or others (e.g., suicidal/homicidal ideation or attempt, acute psychosis) OR Causing inability to perform basic self-care functions
Altered Mental Status For Dementia, see Cognitive and Behavioral/Attentional Disturbance (including dementia and ADD)	Changes causing no or minimal interference with usual social & functional activities	Mild lethargy or somnolence causing greater than minimal interference with usual social & functional activities	Confusion, memory impairment, lethargy, or somnolence causing inability to perform usual social & functional activities	Delirium OR obtundation, OR coma
Ataxia	Asymptomatic ataxia detectable on exam OR Minimal ataxia causing no or minimal interference with usual social & functional activities	Symptomatic ataxia causing greater than minimal interference with usual social & functional activities	Symptomatic ataxia causing inability to perform usual social & functional activities	Disabling ataxia causing inability to perform basic self-care functions
Cognitive and Behavioral/Attentional Disturbance (including dementia and Attention Deficit Disorder)	Disability causing no or minimal interference with usual social & functional activities OR Specialized resources not indicated	Disability causing greater than minimal interference with usual social & functional activities OR Specialized resources on part-time basis indicated	Disability causing inability to perform usual social & functional activities OR Specialized resources on a full-time basis indicated	Disability causing inability to perform basic self-care functions OR Institutionalization indicated
CNS Ischemia (acute)	NA	NA	Transient ischemic attack	Cerebral vascular accident (CVA, stroke) with neurological deficit

NEUROLOGICAL				
	Grade 1	Grade 2	Grade 3	Grade 4
Developmental delay – Pediatric ≤ 16 Years	Mild developmental delay, either motor or cognitive, as determined by comparison with a developmental screening tool appropriate for the setting	Moderate developmental delay, either motor or cognitive, as determined by comparison with a developmental screening tool appropriate for the setting	Severe developmental delay, either motor or cognitive, as determined by comparison with a developmental screening tool appropriate for the setting	Developmental regression, either motor or cognitive, as determined by comparison with a developmental screening tool appropriate for the setting
Headache	Symptoms causing no or minimal interference with usual social & functional activities	Symptoms causing greater than minimal interference with usual social & functional activities	Symptoms causing inability to perform usual social & functional activities	Symptoms causing inability to perform basic self-care functions OR Hospitalization indicated (other than ER visit) OR Headache with significant impairment of alertness or other neurologic function
Insomnia	NA	Difficulty sleeping causing greater than minimal interference with usual social/functional activities	Difficulty sleeping causing inability to perform usual social & functional activities	Disabling insomnia causing inability to perform basic self-care functions
Neuromuscular Weakness (including myopathy & neuropathy)	Asymptomatic with decreased strength on exam OR Minimal muscle weakness causing no or minimal interference with usual social & functional activities	Muscle weakness causing greater than minimal interference with usual social & functional activities	Muscle weakness causing inability to perform usual social & functional activities	Disabling muscle weakness causing inability to perform basic self-care functions OR Respiratory muscle weakness impairing ventilation
Neurosensory Alteration (including paresthesia and painful neuropathy)	Asymptomatic with sensory alteration on exam or minimal paresthesia causing no or minimal interference with usual social & functional activities	Sensory alteration or paresthesia causing greater than minimal interference with usual social & functional activities	Sensory alteration or paresthesia causing inability to perform usual social & functional activities	Disabling sensory alteration or paresthesia causing inability to perform basic self-care functions

NEUROLOGICAL				
	Grade 1	Grade 2	Grade 3	Grade 4
Seizure: (new onset)	NA	1 seizure	2–4 seizures	Seizures of any kind that are prolonged, repetitive (e.g., status epilepticus), or difficult to control (e.g., refractory epilepsy)
Seizure: (pre-existing) For Worsening of Existing Epilepsy the Grades Should Be Based on an Increase from Previous Level of Control to Any of These Levels	NA	Increased frequency of pre-existing seizures (non-repetitive) without change in seizure character OR infrequent breakthrough seizures while on stable meds in a previously controlled seizure disorder	Change in seizure character from baseline either in duration or quality (e.g., severity or focality)	Seizures of any kind that are prolonged, repetitive (e.g., status epilepticus), or difficult to control (e.g., refractory epilepsy)
Seizure – Pediatric < 18 Years	Seizure, generalized onset with or without secondary generalization, lasting < 5 minutes with < 24 hours post ictal state	Seizure, generalized onset with or without secondary generalization, lasting 5-20 minutes with < 24 hours post ictal state	Seizure, generalized onset with or without secondary generalization, lasting > 20 minutes	Seizure, generalized onset with or without secondary generalization, requiring intubation and sedation
Syncope (not associated with a procedure)	NA	Present	NA	NA
Vertigo	Vertigo causing no or minimal interference with usual social & functional activities	Vertigo causing greater than minimal interference with usual social & functional activities	Vertigo causing inability to perform usual social & functional activities	Disabling vertigo causing inability to perform basic self-care functions

MUSCULOSKELETAL				
	Grade 1	Grade 2	Grade 3	Grade 4
Arthralgia See also Arthritis	Joint pain causing no or minimal interference with usual social & functional activities	Joint pain causing greater than minimal interference with usual social & functional activities	Joint pain causing inability to perform usual social & functional activities	Disabling joint pain causing inability to perform basic self-care functions
Arthritis See also Arthralgia	Stiffness or joint swelling causing no or minimal interference with usual social & functional activities	Stiffness or joint swelling causing greater than minimal interference with usual social & functional activities	Stiffness or joint swelling causing inability to perform usual social & functional activities	Disabling joint stiffness or swelling causing inability to perform basic self-care functions
Bone Mineral Loss  Pediatric < 21 Years	BMD t-score or z-score -2.5 to -1.0  BMD z-score -2.5 to -1.0	BMD t-score or z-score < -2.5  BMD z-score < -2.5	Pathological fracture (including loss of vertebral height)  Pathological fracture (including loss of vertebral height)	Pathologic fracture causing life-threatening consequences  Pathologic fracture causing life-threatening consequences
Myalgia (non-injection site)	Muscle pain causing no or minimal interference with usual social & functional activities	Muscle pain causing greater than minimal interference with usual social & functional activities	Muscle pain causing inability to perform usual social & functional activities	Disabling muscle pain causing inability to perform basic self-care functions
Osteonecrosis	NA	Asymptomatic with radiographic findings AND No operative intervention indicated	Symptomatic bone pain with radiographic findings OR Operative intervention indicated	Disabling bone pain with radiographic findings causing inability to perform basic self-care functions

SYSTEMIC				
	Grade 1	Grade 2	Grade 3	Grade 4
Acute Systemic Allergic Reaction	Localized urticaria (wheals) with no medical intervention indicated	Localized urticaria with medical intervention indicated OR Mild angioedema with no medical intervention indicated	Generalized urticaria OR Angioedema with medical intervention indicated OR Symptomatic mild bronchospasm	Acute anaphylaxis OR Life-threatening bronchospasm OR laryngeal edema
Chills	Symptoms causing no or minimal interference with usual social & functional activities	Symptoms causing greater than minimal interference with usual social & functional activities	Symptoms causing inability to perform usual social & functional activities	NA
Fatigue Malaise	Symptoms causing no or minimal interference with usual social & functional activities	Symptoms causing greater than minimal interference with usual social & functional activities	Symptoms causing inability to perform usual social & functional activities	Incapacitating fatigue/malaise symptoms causing inability to perform basic self-care functions
Fever (nonaxillary)	37.7°C to 38.6°C 99.8°F to 101.5°F	38.7°C to 39.3°C 101.6°F to 102.8°F	39.4°C to 40.5°C 102.9°F to 104.9°F	> 40.5°C > 104.9°F
Pain- Indicate Body Site See also Injection Site Pain, Headache, Arthralgia, and Myalgia	Pain causing no or minimal interference with usual social & functional activities	Pain causing greater than minimal interference with usual social & functional activities	Pain causing inability to perform usual social & functional activities	Disabling pain causing inability to perform basic self-care functions OR Hospitalization (other than ER visit) indicated
Unintentional Weight Loss	NA	5% to 9% loss in body weight from baseline	10% to 19% loss in body weight from baseline	≥ 20% loss in body weight from baseline OR Aggressive intervention indicated [e.g., tube feeding or total parenteral nutrition]

INJECTION SITE REACTION				
	Grade 1	Grade 2	Grade 3	Grade 4
Injection Site Pain (pain without touching) Or Tenderness (pain when area is touched)	Pain/tenderness causing no or minimal limitation of use of limb	Pain/tenderness limiting use of limb OR Pain/tenderness causing greater than minimal interference with usual social & functional activities	Pain/tenderness causing inability to perform usual social & functional activities	Pain/tenderness causing inability to perform basic self-care function OR Hospitalization (other than ER visit) indicated for management of pain/tenderness
Injection Site Reaction (Localized), > 15 Years  Pediatric ≤ 15 Years	Erythema OR Induration of 5 × 5 cm to 9 × 9 cm (or 25–81 × cm  )  Erythema OR Induration OR Edema present but ≤ 2.5 cm diameter	Erythema OR Induration OR Edema > 9 cm any diameter (or > 81 cm  )  Erythema OR Induration OR Edema > 2.5 cm diameter but < 50% surface area of the extremity segment (e.g., upper arm/thigh)	Ulceration OR Secondary infection OR Phlebitis OR Sterile abscess OR Drainage  Erythema OR Induration OR Edema involving ≥ 50% surface area of the extremity segment (e.g., upper arm/thigh) OR Ulceration OR Secondary infection OR Phlebitis OR Sterile abscess OR Drainage	Necrosis (involving dermis and deeper tissue)  Necrosis (involving dermis and deeper tissue)
Pruritis Associated with Injection See also Skin: Pruritis (itching—no skin lesions)	Itching localized to injection site AND Relieved spontaneously or with < 48 h treatment	Itching beyond the injection site but not generalized OR Itching localized to injection site requiring ≥ 48 h treatment	Generalized itching causing inability to perform usual social & functional activities	NA

ENDOCRINE/METABOLIC				
	Grade 1	Grade 2	Grade 3	Grade 4
Lipodystrophy (e.g., back of neck, breasts, abdomen)	Detectable by study participant or caregiver (for young children and disabled adults)	Detectable on physical exam by health care provider	Disfiguring OR Obvious changes on casual visual inspection	NA
Diabetes Mellitus	NA	New onset without need to initiate medication OR Modification of current meds to regain glucose control	New onset with initiation of indicated med OR Diabetes uncontrolled despite treatment modification	Life-threatening consequences (e.g., ketoacidosis, hyperosmolar non-ketotic coma)
Gynecomastia	Detectable by study participant or caregiver (for young children and disabled adults)	Detectable on physical exam by health care provider	Disfiguring OR Obvious on casual visual inspection	NA
Hyperthyroidism	Asymptomatic	Symptomatic causing greater than minimal interference with usual social & functional activities OR Thyroid suppression therapy indicated	Symptoms causing inability to perform usual social & functional activities OR Uncontrolled despite treatment modification	Life-threatening consequences (e.g., thyroid storm)
Hypothyroidism	Asymptomatic	Symptomatic causing greater than minimal interference with usual social & functional activities OR Thyroid replacement therapy indicated	Symptoms causing inability to perform usual social & functional activities OR Uncontrolled despite treatment modification	Life-threatening consequences (e.g., myxedema coma)
Lipoatrophy (e.g., fat loss from the face, extremities, buttocks)	Detectable by study participant or caregiver (for young children and disabled adults)	Detectable on physical exam by health care provider	Disfiguring OR Obvious on casual visual inspection	NA

GENITOURINARY				
	Grade 1	Grade 2	Grade 3	Grade 4
Intermenstrual Bleeding (IMB)	Spotting observed by participant OR Minimal blood observed during clinical or colposcopic exam	Intermenstrual bleeding not greater in duration or amount than usual menstrual cycle	Intermenstrual bleeding greater in duration or amount than usual menstrual cycle	Hemorrhage with life-threatening hypotension OR Operative intervention indicated
Urinary Tract obstruction (e.g., stone)	NA	Signs or symptoms of urinary tract obstruction without hydronephrosis or renal dysfunction	Signs or symptoms of urinary tract obstruction with hydronephrosis or renal dysfunction	Obstruction causing life-threatening consequences

INFECTION				
	Grade 1	Grade 2	Grade 3	Grade 4
Infection (any other than HIV infection)	Localized, no systemic antibiatic treatment indicated AND Symptoms causing no or minimal interference with usual social & functional activities	Systemic antibiatic treatment indicated OR Symptoms causing greater than minimal interference with usual social & functional activities	Systemic antibiatic treatment indicated AND Symptoms causing inability to perform usual social & functional activities OR Operative intervention (other than simple incision and drainage) indicated	Life-threatening consequences (e.g., septic shock)

**Basic Self-care Functions:** Activities such as bathing, dressing, toileting, transfer/movement, continence, and feeding.

**Usual Social & Functional Activities:** Adaptive tasks and desirable activities, such as going to work, shopping, cooking, use of transportation, pursuing a hobby, etc

## **Appendix 4. Pregnancy Precautions, Definition for Female of Childbearing Potential, and Contraceptive Requirements**

### **1) Definitions**

#### **a. Definition of Childbearing Potential**

For the purposes of this study, a female born subject is considered of childbearing potential following the initiation of puberty (Tanner stage 2) until becoming post-menopausal, unless permanently sterile or with medically documented ovarian failure.

Women are considered to be in a postmenopausal state when they are  $\geq 54$  years of age with cessation of previously occurring menses for  $\geq 12$  months without an alternative cause. Permanent sterilization includes hysterectomy, bilateral oophorectomy, or bilateral salpingectomy in a female subject of any age.

#### **b. Definition of Male Fertility**

For the purposes of this study, a male born subject is considered of fertile after the initiation of puberty unless permanently sterile by bilateral orchiectomy or medical documentation.

### **2) Contraception Requirements for Female Subjects**

#### **a. Study Drug Effects on Pregnancy and Hormonal Contraception**

##### GS-9992

The risk of treatment with GS-9992 has not been evaluated in pregnant women. Relevant non-clinical reproductive toxicity studies for human pregnancy do not indicate a strong suspicion of human teratogenicity/fetotoxicity. Non-clinical early embryonic development and fertility studies with GS-9992 have not been conducted to date. GS-9992 has insufficient data to exclude the possibility of a clinically relevant interaction with hormonal contraception that results in reduced contraception efficacy. Therefore, contraceptive steroids are not recommended as a contraceptive method either solely or as a part of a contraceptive regimen. Pregnancy tests will be performed regularly throughout this study. Please refer to the latest version of the investigator's brochure for additional information.

##### TAF

Data from clinical pharmacokinetic interaction studies of TAF have demonstrated that there is no reduction in the clinical efficacy of hormonal contraception. Non-clinical toxicity studies in animals (rats and rabbits) of TAF have demonstrated no adverse effect on fertility or embryo-fetal development. However, there are no clinical studies of TAF in pregnant women. Please refer to the latest version of the Investigator's Brochure for additional information.

## **b. Contraception Requirements for Female Subjects of Childbearing Potential**

The inclusion of female subjects of childbearing potential requires the use of highly effective or an acceptable contraceptive measures. They must also not rely on hormone-containing contraceptives as a form of birth control during the study. They must have a negative serum pregnancy test at Screening and a negative pregnancy test on the Baseline/Day 1 visit prior to randomization. At minimum, a pregnancy test will be performed at 4 weeks post-treatment. In the event of a delayed menstrual period (over one month between menstruations), a pregnancy test must be performed to rule out pregnancy. This is even true for women of childbearing potential with infrequent or irregular periods. Female subjects must agree to one of the following from Screening until 7 days after the last dose of TAF and until 90 days after the last dose of GS-9992.

Highly effective contraceptive measures:

- Complete abstinence from intercourse of reproductive potential. Abstinence is an acceptable method of contraception only when it is in line with the subject's preferred and usual lifestyle.

Or

- Consistent and correct use of 1 of the following methods of birth control listed below.
  - Intrauterine device (IUD) with a failure rate of < 1% per year
  - Tubal sterilization
  - Essure micro-insert system (provided confirmation of success 3 months after procedure)
  - Vasectomy in the male partner (provided that the partner is the sole sexual partner and had confirmation of surgical success 3 months after procedure)

Or, Acceptable contraceptive measures:

- Barrier methods (one female barrier and one male barrier must be used in combination)
  - Female barriers: Diaphragm with spermicide or Cervical cap with spermicide
  - Male barriers: Male condom (with or without spermicide)

Female subjects must also refrain from egg donation and in vitro fertilization during treatment and until 7 days after the last dose of TAF and until 90 days after the last dose of GS-9992.

### **3) Contraception Requirements for Male Subjects**

During the study, male subjects with female partners of childbearing potential should use condoms when engaging in intercourse of reproductive potential during treatment with TAF and for 90 days after the last dose of GS-9992.

Male subjects must also refrain from sperm donation during treatment with GS-9992 and until 90 days after the end of last dose of GS-9992.

#### **Unacceptable Birth Control Methods**

Birth control methods that are unacceptable include periodic abstinence (e.g., calendar, ovulation, symptothermal, post-ovulation methods), withdrawal (coitus interruptus), spermicides only, and lactational amenorrhea method (LAM). Female condom and male condom should not be used together.

### **4) Procedures to be Followed in the Event of Pregnancy**

Subjects will be instructed to notify the investigator if they become pregnant at any time during the study, or if they become pregnant within 30 days of last study drug dose. Subjects who become pregnant or who suspect that they are pregnant during the study must report the information to the investigator and discontinue study drug immediately. Subjects whose partner has become pregnant or suspects she is pregnant during the study must report the information to the investigator. Instructions for reporting pregnancy, partner pregnancy, and pregnancy outcome are outlined in Section [7.7.2.1](#).

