### 4.2. Groups 1-3 and 5 Inclusion Criteria

Subjects must meet all of the following inclusion criteria to be eligible for participation in this study:

- 1) Ability to understand and sign a written informed consent form, which must be obtained prior to initiation of study procedures.
- 2) Aged 18 to 70 years of age, inclusive, based on the date of screening visit.
- 3) Females of childbearing potential (as defined in [Appendix 4](#)) must have a negative serum pregnancy test at screening and a negative urine test at Baseline before dosing.
- 4) Male subjects and female subjects of childbearing potential who engage in heterosexual intercourse must agree to use protocol specified method(s) of contraception until 90 days after the last dose of GS-9992 and as described in [Appendix 4](#).
- 5) Chronic hepatitis B infection defined as, HBsAg or HBV DNA positivity for at least 6 months prior to the Baseline visit, or medical records indicating a chronic HBV infection, and meeting the following criteria.
  - a) Screening HBV DNA  $\geq 2 \times 10^4$  IU/mL for HBeAg-positive subjects
  - b) Screening HBV DNA  $\geq 2 \times 10^3$  IU/mL for HBeAg-negative subjects
  - c) Screening serum ALT level  $> 35$  U/L (males) or  $> 25$  U/L (females) and  $\leq 5 \times$  ULN (by central laboratory range).
- 6) Subjects not taking any prescribed HBV NUC treatment for at least 3 months prior to the Baseline visit.
- 7) Screening ECG without clinically significant abnormalities, including QTcF interval (QT corrected using Fridericia's formula)  $< 450$  msec for males and  $< 470$  msec for females.
- 8) Must be willing and able to comply with all study requirements.

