## **7.7.2. Instructions for Reporting Special Situations**

### **7.7.2.1. Instructions for Reporting Pregnancies**

The investigator should report pregnancies in female study subjects that are identified after initiation of study medication and throughout the study, including the post study drug follow-up period, to Gilead PVE using the pregnancy report form within 24 hours of becoming aware of the pregnancy.

Refer to Section 7.3 and the eCRF completion guidelines for full instructions on the mechanism of pregnancy reporting.

The pregnancy itself is not considered an AE nor is an induced elective abortion to terminate a pregnancy without medical reasons.

Any premature termination of pregnancy (e.g., a spontaneous abortion, an induced therapeutic abortion due to complications or other medical reasons) must be reported within 24 hours as an SAE. The underlying medical reason for this procedure should be recorded as the AE term.

A spontaneous abortion is always considered to be an SAE and will be reported as described in Sections 7.1.1 and 7.1.2. Furthermore, any SAE occurring as an adverse pregnancy outcome post study must be reported to Gilead PVE.

The subject should receive appropriate monitoring and care until the conclusion of the pregnancy. The outcome should be reported to Gilead PVE using the pregnancy outcome report form. If the end of the pregnancy occurs after the study has been completed, the outcome should be reported directly to Gilead PVE. Gilead PVE contact information is as follows:

Email: **PPD** and Fax: **PPD**.

Pregnancies of female partners of male study subjects exposed to Gilead or other study drugs must also be reported and relevant information should be submitted to Gilead PVE using the pregnancy and pregnancy outcome forms within 24 hours. Monitoring of the subject should continue until the conclusion of the pregnancy. If the end of the pregnancy occurs after the study has been completed, the outcome should be reported directly to Gilead PVE, fax number PPD or email PPD.

Refer to [Appendix 4](#) for Pregnancy Precautions, Definition for Female of Childbearing Potential, and Contraceptive Requirements.

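### Where a GS-9992 recipient's participation ends early, the duty to notify a pregnancy can end before the 90-day contraception period: by 0 to 60 days for women, and by up to 90 days for partners of men

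*Protocol*

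**What the plan says.** **Contraception.** Inclusion criterion 4, in Section 4.2 (Groups 1-3 and 5) and again in Section 4.4 (Group 4), says that male subjects and women of childbearing potential "must agree to use protocol specified method(s) of contraception until 90 days after the last dose of GS-9992". Protocol Appendix 4, item 2b, sets the period for women "until 7 days after the last dose of TAF and until 90 days after the last dose of GS-9992". Item 3 asks male subjects to use condoms "during treatment with TAF and for 90 days after the last dose of GS-9992".

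**Notification by the subject.** Appendix 4, item 4, has a female subject tell the investigator of a pregnancy at any time in the study "or if they become pregnant within 30 days of last study drug dose". For partners it says: "Subjects whose partner has become pregnant or suspects she is pregnant during the study must report the information to the investigator". No period after the study or after the last dose is given for partners.

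**Reporting by the investigator.** Section 7.7.2.1 covers pregnancies in female subjects identified "after initiation of study medication and throughout the study, including the post study drug follow-up period". For partners it says: "Pregnancies of female partners of male study subjects exposed to Gilead or other study drugs must also be reported", with no time limit. After the study it adds serious adverse events that are adverse pregnancy outcomes.

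**Follow-up.** Under Section 3.4, GS-9992 is given for 12 weeks and all subjects are followed to Week 48. Under Section 3.2, subjects who stop all HBV therapy are followed for 24 weeks, or until alternative CHB therapy starts if that is sooner.

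**The concern.** The protocol treats the 90 days after GS-9992 as a period in which pregnancy is to be avoided, for both sexes. The same appendix then sets a shorter notification period for subjects and gives no reason for the difference. A subject who follows item 4 to the letter could leave, become pregnant inside the 90 days, and have no stated duty to tell anyone.

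At stake is whether the sponsor learns of pregnancies that begin inside its own precaution period. Appendix 4, item 2a, says that GS-9992 has not been evaluated in pregnant women and that early embryonic development and fertility studies have not been done. The same paragraph says that the relevant non-clinical studies raise no strong suspicion of harm to a human fetus. The concern therefore rests on the protocol's own 90-day rule, not on a known hazard.

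Early exit is a realistic case. Sections 6.6 and 6.10 allow withdrawal. Section 1.2.2 reports that in the 50 mg cohort of the earlier Phase 2 trial (16 active subjects, since 11 are given as 68.8%), one subject stopped drug and left the study at Week 2.

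**Working it through.** The plan gives no figure for this gap, so there is nothing to reproduce. The check is day arithmetic.

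**Inputs**
- Contraception ends 90 days after the last GS-9992 dose (Sections 4.2 and 4.4; Appendix 4, items 2b and 3).
- A woman's duty to notify lasts to the end of her participation or to 30 days after her last study drug dose, whichever is later (Appendix 4, item 4).
- Study drugs are GS-9992 and TAF (SAP Section 3.1.2). Continued TAF therefore extends the 30 days. A Group 4 subject's own NUC does not.
- A male subject's duty on partner pregnancies lasts to the end of his participation (Appendix 4, item 4).
- GS-9992 is given for 12 × 7 = 84 days (Section 3.4). Treatment-free follow-up is 24 × 7 = 168 days (Section 3.2).

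**Formulas.** Let G be the day of the last GS-9992 dose, L the day of the last dose of either study drug, and X the day participation ends.
- Women: uncovered days = max(0, (G + 90) − max(X, L + 30)).
- Partners of men, subject's side: uncovered days = max(0, (G + 90) − X).

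**Cases with no gap**
- Week 48 completers: 336 − 84 = 252 days of participation after GS-9992, more than 90.
- Full treatment-free follow-up: 168 days, more than 90.
- Group 2: no GS-9992, so the 90-day rule does not arise.

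**All study drug stopped and study left on the same day, any G.** Women: (G + 90) − (G + 30) = 60 days, which is 60/90 = 67% of the period. Partners: (G + 90) − G = 90 days.

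**GS-9992 completed on Day 84.** The contraception period ends on Day 84 + 90 = 174.
- Groups 1, 3 and 5, on TAF until exit (L = X): 174 − (X + 30) = 144 − X.
- Group 4, or all study drug stopped at Day 84 (L = 84): 174 − max(X, 114).
- Partners of men: 174 − X.

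| Exit day X | Women, Groups 1, 3, 5 on TAF to exit | Women, Group 4 or all study drug stopped at Day 84 | Partners, subject's side |
|---|---|---|---|
| 84 | 60 | 60 | 90 |
| 100 | 44 | 60 | 74 |
| 120 | 24 | 54 | 54 |
| 144 | 0 | 30 | 30 |
| 169 | 0 | 5 | 5 |
| 174 | 0 | 0 | 0 |

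**Follow-up cut short by alternative CHB therapy.** If all study drug stops together and follow-up ends k days later, a woman's gap is 90 − max(k, 30), with a floor of 0: 60 days for k up to 30, 30 days at k = 60, and 0 from k = 90. A gap can therefore arise without withdrawal.

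**Do other provisions fill the gap?** The scheduled pregnancy test in treatment-free follow-up is at Week 4 (Section 6.5). The early discontinuation visit falls within 14 days of notice (Section 6.6), so for a subject who leaves at the last dose it comes before day 31. Section 7.7.2.1 binds the investigator, who depends on what the subject discloses.

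**The case against.** The strongest reply is that the design already covers nearly everyone. The 30 days are added to a duty that runs throughout the study, and they run from the last dose of either study drug. Sites are told to try to keep subjects who stop dosing, and pregnancy tests are scheduled at every visit to Week 48 and at early discontinuation. All of this stands, and it limits the point to GS-9992 recipients whose participation ends early.

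It can also be said that contraception and pregnancy reporting are separate obligations, so different durations are not in themselves a contradiction. That is fair in principle. Here, however, the protocol gives no reason for the difference, and followed as written the rules leave days in the contraception period with no duty on the subject to notify.

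Three stronger readings are tempting, and the documents support none of them.
- **That pregnancies in days 31 to 90 are lost for anyone who leaves early.** The gap is 0 to 60 days for women, and many early leavers have none. Serious adverse pregnancy outcomes stay reportable after the study (Section 7.7.2.1), as do serious events the investigator learns of and considers relevant to study drug (Section 7.3). Partner pregnancies carry no time limit for the investigator. What is missing is the instruction to the subject.
- **That a conception in those days is an exposed pregnancy.** The protocol sets a contraception period; it does not call days 31 to 90 a period of exposure. The longest mean plasma half-life given for the metabolites in Section 1.2.2 is 19.3 hours. That neither shows exposure at that distance nor settles which period is right.
- **That the consent form has the same defect.** The consent pages are not available here, so their wording cannot be judged.

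**Conclusion.** The point holds in a narrow form. The 90-day contraception period and the notification periods in Appendix 4 do not agree, and neither Section 7.7.2.1 nor Section 7.3 gives a subject who has left a duty to report in the remaining days.

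For women given GS-9992 whose participation ends early, 0 to 60 of the 90 days are uncovered. For partners of male subjects, up to 90 days are uncovered on the subject's side only. The closing days of about 144 and 174 assume a full 84 days of GS-9992; an earlier stop moves them earlier.

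The number affected is not given. The plan has about 30 + 30 + 20 + 30 = 110 GS-9992 recipients, and only women of childbearing potential, or men with partners of childbearing potential, who leave early could be concerned. That this is few people is a judgement, since the documents give no expected dropout rate. No efficacy or safety analysis depends on it. It is a minor point, worth raising because the correction is cheap.

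**What to change.** Reconcile Appendix 4 (items 2b, 3 and 4) and Section 7.7.2.1, together with inclusion criterion 4 in Sections 4.2 and 4.4, so that the contraception period and the notification periods for subjects and partners are consistent. The sponsor should choose the period; this review does not say which is right. The text should state which drug's last dose starts the clock, and that the duty continues after a subject leaves the study or after follow-up ends because alternative CHB therapy has begun. It should also give an end point for partner pregnancies. With matching periods, the uncovered days fall to 0 in every case worked above.

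The cost is about one sentence in Appendix 4, with a check that Section 7.7.2.1 and the subject-facing wording agree with it. No visit or test is added.
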